13 SOURCE DOCUMENTS AND ACCESS TO SOURCE DATA/DOCUMENTS

Source documents will include signed consent forms kept at the local study site, as well as the REDCap database which is web based. Study staff will maintain appropriate research records for this study, in compliance with ICH E6, Section 4.9 and regulatory and institutional requirements for the protection of confidentiality of participants. Study staff will permit authorized representatives of NIDCR and regulatory agencies to examine (and when required by applicable law, to copy) research records for the purposes of quality assurance reviews, audits, and evaluation of the study safety, progress, and data validity.

14 QUALITY CONTROL AND QUALITY ASSURANCE

PHI will be collected and stored on subjects enrolled at Duke. All potential subjects who are approached about study participation will be entered in a screening log. Those who agree to participate by providing written informed consent will be entered in the enrollment log and assigned a unique study ID number. Identifiers such as name, medical record number and date of study visit will be included in the enrollment log and the REDCap database. If electronic consent is obtained then email address will also be collected. Quality reviews will be done by the PI and study team on a weekly basis, and per the independent internal monitor as outlined in the CQMP. The PI and Study Coordinator (SC) will be responsible for correcting procedures that are not in compliance with protocol and quality control issues (correcting errors in data entry).

A kick-off meeting will be conducted to train study staff on the protocol and use of FNS device prior to start of study activities.

The Industry partner will assess the quality of the scopes prior and during usage. The industry partner will provide adequate support for repair or replacement as needed.

15 ETHICS/PROTECTION OF HUMAN SUBJECTS

15.1 Ethical Standard

The investigator will ensure that this study is conducted in full conformity with the principles set forth in The Belmont Report: Ethical Principles and Guidelines for the Protection of Human Subjects of Research, as drafted by the US National Commission for the Protection of Human Subjects of Biomedical and Behavioral Research (April 18, 1979) and codified in 45 CFR Part 46 and/or the ICH E6, the Declaration of Helsinki, and the International Ethical Guidelines for Biomedical Research Involving Human Subjects (2002).

15.2 Institutional Review Board

Review and approval of this protocol and the associated informed consent documents and recruitment materials by an appropriate IRB registered with the OHRP will be obtained. Duke University Health System IRB will be the IRB of record for the optimization phase. The FWA number assigned to Duke's IRB is FWA00009025, expiring 2/11/2027.

The protocol, informed consent form(s), and all participant materials will be submitted to the IRB for review and approval. Approval of both the protocol and the consent form(s) must be obtained before any participant is enrolled. Amendments to the protocol will require review and approval by the IRB and NIDCR before the changes are implemented in the study.

15.3 Informed Consent Process

Informed consent is a process that is initiated prior to the individual agreeing to participate in the study and continues throughout study participation. Written informed consent will be obtained by paper or electronic consent. An oral explanation of the study will be given to the potential subjects, and they will be asked to also read and sign the consent form. A copy will be provided to them. If electronic consent is obtained then an electronic copy will be automatically sent to the participants email address. Consent forms will be IRB-approved, and the participant is required to be able to read and review the document. The investigator or designee will explain the research study to the participant and answer any questions that may arise. The participant will sign the informed consent document prior to any study-related assessments or procedures. Participants will be given the opportunity to discuss the study with their surrogates or think about it prior to agreeing to participate. They may withdraw consent at any time during the course of the study. The rights and welfare of the participants will be protected by emphasizing to them that the quality of their clinical care will not be adversely affected if they decline to participate in this study.

The consent process will be documented in the electronic health record.

15.4 Exclusion of Women, Minorities, and Children (Special Populations)

There are no exclusionary criteria for the study population based on sex/gender, race, or ethnic background. As this is a focused device study on a new low-cost FNS, there is no scientific reason to exclude any subject by sex/gender, race or ethnic group, or pregnancy status. We are excluding children as head and neck cancers are very rare in this population.

15.5 Subject Confidentiality

Subject confidentiality is strictly held in trust by the investigators, study staff, and the study sponsor(s) and their agents.

The study protocol, documentation, data, and all other information generated will be held in strict confidence. No information concerning the study or the data will be released to any unauthorized third party without prior written approval of the study sponsor.

The study monitor or other authorized representatives of NIDCR may inspect all study documents and records required to be maintained by the investigator, including but not limited to source documents and survey responses for the study participants. The clinical study site will permit access to such records.

Certificate of Confidentiality

To further protect the privacy of study participants, the Secretary, Health and Human Services (HHS), has issued a Certificate of Confidentiality (CoC) to all researchers engaged in biomedical, behavioral, clinical, or other human subjects research funded wholly or in part by the federal government. Recipients of NIH funding for human subjects research are required to protect identifiable research information from forced disclosure per the terms of the NIH Policy (<https://humansubjects.nih.gov/coc/index>). As set forth in [45 CFR Part 75.303\(a\)](#) and [NIHGPS Chapter 8.3](#), recipients conducting NIH-supported research covered by this Policy are required to establish and maintain effective internal controls (e.g., policies and procedures) that provide reasonable assurance that the award is managed in compliance with Federal statutes, regulations, and the terms and conditions of award. It is the NIH policy that investigators and others who have access to research records will not disclose identifying information except when the participant consents or in certain instances when federal, state, or local law or regulation requires disclosure. NIH expects investigators to inform research participants of the protections and the limits to protections provided by a Certificate issued by this Policy.

NIH Data Sharing Policies

As described in section 17, it is NIH policy that the results and accomplishments of the activities that it funds should be made available to the public (see <https://grants.nih.gov/policy/sharing.htm>). PIs and funding recipient institutions will

ensure that all mechanisms used to share data include proper plans and safeguards to protect the rights and privacy of individuals who participate in NIH-sponsored research.

16 DATA HANDLING AND RECORD KEEPING

The investigators are responsible for ensuring the accuracy, completeness, legibility, and timeliness of the data reported. All source documents should be completed in a neat, legible manner to ensure accurate interpretation of data. The investigators will maintain adequate case histories of study participants, including accurate case report forms (CRFs), and source documentation.

16.1 Data Management Responsibilities

Data collection and accurate documentation are the responsibility of the study staff under the supervision of the investigator. All source documents must be reviewed by the study team and data entry staff, who will ensure that they are accurate and complete. Unanticipated problems and adverse events must be reviewed by the investigator or designee.

16.2 Data Capture Methods

The team will work with the research staff to develop a REDCap EDC that meets the data collection needs for the project. Data being collected for this project does not include identifiable information. The data will be stored in a HIPAA Compliant EDC. A member of the Clinical Data Management Team will have access to the data as outlined above for the duration of the project in order to oversee data security and data integrity on behalf of the Department and the Study Team.

16.3 Types of Data

Data containing PHI will be stored locally in the Duke REDCap database and the electronic screening/enrollment logs; PHI will include name, medical record number, email address, and date of visit. Survey data will include health care providers assessment of the prototype's 1) Ease of use and 2) quality of images. This will also include assessment of adverse events.

Furthermore, subjective pain comparison between the SOC and prototype scopes will be collected from the subject and study investigator via a tablet.

Data review and reports will occur at least twice a year or more frequently based on the final CQMP plan approved by the Duke School of Medicine's Office of Clinical Research from site visits by the independent medical monitor. Protocol and data review will occur during internal monitoring per the CQMP guidance document. Reporting enrollment schedule to the NIDCR will be determined by NIDCR and NIDCR appointed DSMB.

16.4 SCHEDULE AND CONTENT OF REPORTS

Data review and reports will occur at least twice a year from clinical site monitoring activities, as described under protocol section 11. Protocol and data review will also occur prior to DSMB reporting. The specific schedule or reporting will be determined by NIDCR and the NIDCR appointed DSMB.

16.5 Study Records Retention

Study records will be maintained for a minimum of six years following the completion of the study (closure with the IRB), or a minimum of 2 years after the last approval of a marketing application in an ICH region and until there are no pending, or contemplated marketing applications in an ICH region, or until at least 2 years have elapsed since the formal discontinuation of clinical development of the investigational product (whichever is longer). These documents should be retained for a longer period, however, if required by local regulations. No records will be destroyed without the written consent of the sponsor, if applicable. It is the responsibility of the sponsor to inform the investigator when these documents no longer need to be retained.

16.6 Protocol Deviations

A protocol deviation is any noncompliance with the clinical study protocol or Good Clinical Practice requirements. The noncompliance may be on the part of the participant, the investigator, or study staff. As a result of deviations, corrective actions are to be developed by the study staff and implemented promptly.

These practices are consistent with investigator and sponsor obligations in ICH E6.

All deviations from the protocol must be addressed in study participant source documents and promptly reported to NIDCR and the IRB, according to their requirements.

17 PUBLICATION/DATA SHARING

This study will comply with all applicable NIH Data Sharing Policies. See <https://grants.nih.gov/policy/sharing.htm> for policies and resources.

NIH Public Access Policy

The NIH *Public Access Policy* requires scientists to submit final peer-reviewed journal manuscripts that arise from NIH funds to *PubMed Central* immediately upon acceptance for publication. This ensures that the public has access to the published results of NIH funded research.

Piker, E. G., Schulz, K., Parham, K., Vambutas, A., Witsell, D., Tucci, D., Lee, W. T. (2016). Variation in the Use of Vestibular Diagnostic Testing for Patients Presenting to Otolaryngology Clinics with Dizziness. *Otolaryngol Head Neck Surg*, 155(1), 42-47. doi:10.1177/0194599816650173

Powell, B. J., McMillen, J. C., Proctor, E. K., Carpenter, C. R., Griffey, R. T., Bunger, A. C., Glass, J. E., York, J. L. (2012). A compilation of strategies for implementing clinical innovations in health and mental health. *Med Care Res Rev*, 69(2), 123-57. doi: 10.1177/1077558711430690.

Powell, B. J., Waltz, T. J., Chinman, M. J., Damschroder, L. J., Smith J. L., Matthieu M. M., Proctor, E. K., Kirchner, J. E. (2015). A refined compilation of implementation strategies: results from the Expert Recommendations for Implementing Change (ERIC) project. *Implement Sci*, 12, 10:21. doi: 10.1186/s13012-015-0209-1.

Schroy, P. C., 3rd, Wilson, S., & Afdhal, N. (1996). Feasibility of high-volume screening sigmoidoscopy using a flexible fiberoptic endoscope and a disposable sheath system. *Am J Gastroenterol*, 91(7), 1331-1337.

Vo, Q. T., Pham, D., Choi, K. J., Nguyen, U. T., Le, L., Shanewise, T., Lee, W. T. (2017). Solar-powered hearing aids for children with impaired hearing in Vietnam: a pilot study. *Paediatr Int Child Health*, 1-6. doi:10.1080/20469047.2016.1276119

SUPPLEMENTAL MATERIALS

Post-Procedural Survey By Clinician who performed the scope exam

(Provider questions once the SOC and study FNS exams are completed):

TECHNICAL ASSESSMENT OF FNS

Were you able to complete the first scope procedure to your satisfaction?

1=no 2=somewhat 3=yes

Were you able to complete the second scope procedure to your satisfaction

1=no 2=somewhat 3=yes

Were you able to view all the structures of concern using first scope ? Y/N

If no, please explain:

Were you able to view all the structures of concern using second scope ? Y/N

If no, please explain:

Did the patient appear to have more, the same, or less discomfort with the second scope?

much more about the same much less
1 2 3

If much more: please describe why:

Were there technical issues with the second prototype scope? Y/N (if Yes, please explain below)

- _____ steering
 - _____ lighting
 - _____ video
 - _____ fogging
 - _____ image capture
 - _____ other

Ease of use: Aim 1:

Compared with the first scope, how easy was the second scope to use?

Very hard Harder same Easier Very easy

If harder or very hard: please explain:

Quality of Images: Aim 1

Rate the video quality of the first scope: (Poor) 1 2 3 4 5 (Excellent)

Rate the video quality of the second scope: (Poor) 1 2 3 4 5 (Excellent)

Did the subject experience an AE: Y / N

If yes - please provide additional information below:

Name of adverse event: _____

Brief description of the problem or event:

Severity of adverse event (using scale below):

1. Mild: no intervention required
2. Moderate: minimal, local, or non-invasive intervention indicated
3. Severe: significant symptoms requiring invasive intervention; subject seeks medical attention

Is the adverse event related to study procedure?

1. **If related**, please specify: Possibly, Probably, or Definitely related
 - a) The event is known to occur with the study intervention, and/or
 - b) There is a temporal relationship between the intervention and event onset and/or
 - c) The event abates when the intervention is discontinued, and/or
 - d) The event reappears upon a re-challenge with the intervention.
2. **If not related**, please specify if unlikely related or Not Related)
 - a) There is no temporal relationship between the intervention and event onset, and/or
 - b) An alternate etiology has been established.

Is the problem/event unexpected? Y/N

Does the event meet the definition of a serious adverse event? Y/N

If yes, check criteria below:

A serious adverse event (SAE) is one that meets one or more of the following criteria:

1. Results in death

-
- 2. Is life-threatening (places the subject at immediate risk of death from the event as it occurred)
 - 3. Results in inpatient hospitalization or prolongation of existing hospitalization
 - 4. Results in a persistent or significant disability or incapacity

An important medical event that may not result in death, be life threatening, or require hospitalization may be considered an SAE when, based upon appropriate medical judgment, the event may jeopardize the subject and may require medical or surgical intervention to prevent one of the outcomes listed in this definition.

Outcome of adverse event: resolved or unresolved

Date of resolution:

For enrolled subjects

Pain Comparison: Aim 1-secondary objective

Did you experience more, the same, or less pain/discomfort with the second scope compared with the first scope?

much more about the same much less

1 2 3

CONSENT FORM FOR PARTICIPATING IN RESEARCH

Duke's IRB approved consent form will be provided separately

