3.1 Primary

Objective	Brief Description/Justification of Outcome Measure	Outcome Measured By	Time Frame
Assess ease of use by end users between the SOC scope and FNS	We are comparing the ease of use between the FNS to the SOC scope. This will impact the design considerations and modification for the prototype optimization.	Compared with the first scope, how easy was the second scope to use? Very Hard 1 Harder 2 Same 3 Easier 4 Very Easy 5	Up to 2 months

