4 STUDY DESIGN

The Optimization Phase (Phase 1) Due to new regulatory restrictions in Vietnam, the optimization phase for Aim 1 will now be conducted at Duke University. This will allow us to obtain data from subjects and providers that will be helpful in determining if additional adjustments or improvements are needed to the FNS prototype. Direct comparison between the current approach using available SOC flexible scopes with the new approach using the low cost FNS will be made. Potential eligible subjects being seen in the Duke Head and Neck Surgery and Communication Sciences clinic meeting clinical indication for a SOC scope exam will be approached for the study. If consent is given, the subject will first undergo the “SOC” scope endoscopy. Then the FNS exam will be performed using the prototype. A post-procedure survey will then be administered and completed by both the provider and subject. Post-procedure data will be collected in three areas: technical assessment, physician feedback, and subject feedback.

The entire study procedure after consent takes about 5 minutes: ~one minute for the SOC scope procedure, ~one minute to change to the FNS scope, ~one minute for the FNS procedure, ~one minute to complete the study survey. We will have at least two low cost FNS to use. To allow for high level disinfection (HLD) between use, we will recruit 2 study participants in the morning clinic session, and 2 in the afternoon for a total of 4 participants per day.

Data will be collected using REDCap on a tablet to enable real time data collection. REDCap is a browser-based survey data collection platform. The data input tablet will be password protected and coded. Data will be stored in the REDCap database. Data will be collected after each FNS scope procedure and will include a technical assessment from the physician. This assessment includes ease of use, and quality of the image. Finally, the subjects will use a numeric scale to assess and compare pain experience between the two scope procedures. Collection of adverse events will also be via REDCap at this time.

The study participation is completed on the scope when survey information is collected. Data collection for each FNS prototype will involve a cohort of up to 50 subjects.

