12.3 Final Analysis Plan

Statistical Analysis – Aim 1: Optimization Phase.

1. Outcome 1 (Primary): The primary outcome is ease of use comparison between the FNS to the SOC scope (score of 1 – 5, with 1 being very hard and 5 being very easy).
2. Outcome 2 (Secondary): Quality of the image (image quality score range 1-5, with 1 being poor and 5 being excellent).
3. Outcome 3 (Secondary): Perceived pain between the FNS to the SOC scope (pain score range of 1 – 3, with 1 being much more and 3 being much less).

Scenario 1:

Success of this first phase 1 (Aim 1) after evaluating 37 subjects is defined as - (1) at least 90% response of ease of use of second scope compared to first score to range from same to excellent (3 to 5); and (2) 90% responding to better video quality of second scope compared to first (score ranging from same to excellent (3 to 5); and (3) 90% responding to pain score of same or much less (2 or 3); In short, this phase is a success if 90% respond to same to excellent/much less on all 3 of the outcomes.

[figure not shown]
Scenario 2: If the rate is between 50 to < 90% for any three outcomes in a sample from 37, then the plan is to proceed recruiting more subjects until 50 are recruited. At 50 subjects, if in scenario 1 then phase 1 is a success and phase 1 is complete; if not, fine tune the prototype.

Scenario 3: If the rate is < 50% for any one of the 3 outcomes described above, then the plan is to proceed to fine tuning the prototype.

The primary outcome of ease of use of scope as reported by the physicians, will be examined between the two different scopes, at the simplest level, using paired Z-test if the scores (or transformed scores) are normally distributed or by using Wilcoxon test if the scores are non-normal.

The analysis for secondary outcomes of the change in the quality of the videos and pain will each be examined using paired Z-test, if the change (or transformed scores) is normally distributed or by Wilcoxon test if the change is non-normal. Assumptions of each of these tests will be examined. The significance of each of the outcomes will be examined at alpha = 0.05. The reliability of this instrument (using intra-class-correlation (ICC)) will be first assessed by using the data from the first 50 subjects. If ICC is < 0.9, we will include training component and necessary adjustment for the physicians.

See diagram below

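### The clinician form asks for a written reason only for the two ease-of-use answers that count as failure, which could nudge borderline ratings towards success

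*Combined protocol and SAP*

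**What the plan says.** The survey in the Supplemental Materials is headed "Post-Procedural Survey By Clinician who performed the scope exam". Its primary item reads "Compared with the first scope, how easy was the second scope to use", with the options "Very hard Harder same Easier Very easy". Section 3.1 codes them "Very Hard 1 Harder 2 Same 3 Easier 4 Very Easy 5". The one follow-up to this item is "If harder or very hard: please explain".

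Scenario 1 in section 12.3 sets the ease criterion as "at least 90% response of ease of use of second scope compared to first score to range from same to excellent (3 to 5"). It requires the same 90% level for video quality and for the subject's pain rating, and all three must be met.

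Section 4 budgets about "one minute to complete the study survey". Sections 4 and 7.1 fix the order of exams: standard scope first, FNS second.

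Elsewhere on the form, the clinician's discomfort item has a similar prompt, "If much more: please describe why". The items on structures seen and on technical issues ask for an explanation when there is a problem, whatever the ease rating. The two video ratings and the subject's pain question have no follow-up prompt.

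**The concern.** Asking why a prototype was harder to use is sensible in a study meant to improve it. The difficulty is that the same item is the primary success criterion and is split into success and failure exactly where the writing task begins. A clinician hesitating between 'harder' and 'same' has a small practical reason to choose 'same', and that choice crosses the success boundary. No comparable prompt works in the other direction.

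Three features of the plan leave room for this. The rater is the operator and knows which scope is the prototype. The time allowed is short: nine questions precede the adverse-event question. The same few clinicians complete all the forms. Nothing in the plan offsets the asymmetry, such as an independent rater or a comment field for every answer.

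At stake is the decision to stop modifying the prototype. Section 12.3 judges success on the observed proportion, so one answer can decide it. Once recorded, a softened 'same' cannot be told from a genuine one, so the remedy has to come before data collection.

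**Working it through.** **1. Prompt against success rule.**

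| Ease answer | Code (3.1) | Written reason asked? (form) | Counts as success? (12.3) |
|---|---|---|---|
| Very hard | 1 | Yes | No |
| Harder | 2 | Yes | No |
| Same | 3 | No | Yes |
| Easier | 4 | No | Yes |
| Very easy | 5 | No | Yes |

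Within this item the two splits coincide exactly.

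**2. The plan's own figure.** Section 12.2 gives n = 37 for a 95% interval of width 0.2 at a proportion of 0.9, with limits 0.76 and 0.96. The Wilson interval has

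- centre (p + z²/2n)/(1 + z²/n) = (0.9 + 3.8415/74)/(1 + 3.8415/37) = 0.862
- half-width z·√(p(1−p)/n + z²/4n²)/(1 + z²/n) = 1.96·√(0.09/37 + 3.8415/5476)/1.1038 = 0.099

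The limits are 0.763 and 0.962, width 0.199. At n = 36 the width is 0.202. The stated figures reproduce, and nothing in this point changes them.

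**3. Threshold in counts.** 0.9 × 37 = 33.3, so at least 34 answers of 3 to 5 are needed: 33/37 = 89.2% misses and 34/37 = 91.9% passes. At 50 subjects, 0.9 × 50 = 45.

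**4. Forms per clinician.** Section 5.3 lists two full-time and two part-time surgeons. With an even split (assumed), 37/4 ≈ 9 and 50/4 ≈ 12.5 forms each.

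**5. Illustration.** Let p be the true same-or-better rate and f the share of true 'harder' or 'very hard' ratings recorded as 'same'. Both are assumptions; the documents give neither. The recorded rate is p′ = p + f(1 − p). With p = 0.85, f = 0.10 gives 0.85 + 0.10 × 0.15 = 0.865, and f = 0.25 gives 0.85 + 0.25 × 0.15 = 0.8875. The exact binomial probability P(X ≥ 34 | n = 37, p′) is:

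| True rate p | f = 0 | f = 0.10 | f = 0.25 |
|---|---|---|---|
| 0.80 | 4.5% | 8.0% | 17.4% |
| 0.85 | 17.4% | 24.6% | 38.9% |
| 0.90 | 48.6% | 57.0% | 70.0% |

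Now add the section 12.3 extension, read for ease alone: a result of 19 to 33 out of 37 (50% to below 90%) continues to 50 and passes with at least 45. At p = 0.85 the chances become 25.8%, 35.8% and 54.2%.

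**6. From ease alone to phase success.** Assume, for illustration, that video quality and pain each have a true 90% rate and that the three outcomes are independent. Each of the other two passes at 37 with probability 0.4864, and 0.4864² = 0.2366. Phase success at 37 with p = 0.85 is then 0.1736 × 0.2366 = 4.1% (f = 0), 0.2455 × 0.2366 = 5.8% (f = 0.10) and 0.3893 × 0.2366 = 9.2% (f = 0.25).

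**The case against.** The strongest reply is that the documents show an asymmetric prompt, not a bias. No section gives a rate of softened answers, says that the comment is mandatory, or shows how REDCap displays it. About nine forms per surgeon, at four participants a day, is modest exposure, and the one-minute allowance is approximate. All of this stands. A reader might infer that the form biases the primary outcome; the documents support only that it could.

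A reader might also infer that 'same' is an answer without effort, or that each softened 'harder' loses the feedback needed for the next prototype. Neither follows. Just before the ease item, every clinician is asked about technical issues, with an explanation if there were any, and the form also asks for reasons when structures were not seen. Both apply whatever the ease rating. What could be lost is the reason tied to the ease judgement itself, not all modification feedback.

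The discomfort item invites a further over-reading. The clinician's rating is not a success criterion; the pain outcome is the subject's own answer, which has no prompt. Only one of the three criteria is touched.

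The illustration is also open to challenge. It lets every unfavourable rating soften, including 'very hard', whereas the mechanism concerns borderline ones, and both p and f are assumed. That is why a range is shown.

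Finally, asking for reasons on poor ratings serves the aim in section 4. That is true, and the fix keeps those reasons.

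**Conclusion.** The point holds as a weakness in data collection with a possible one-directional effect. Within the primary item, the answers that call for writing are exactly those that count against the FNS. The rater is unblinded, and success turns on an observed proportion that one answer can move across 90%. Whether any softening would occur, and how much, cannot be learned from the documents.

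Under the assumed 85% true rate, the chance of passing ease alone at 37 rises by about 7 percentage points if 1 in 10 unfavourable ratings softens and by about 22 if 1 in 4 does. These should not be read as changes in the chance of phase success. Under the further assumptions in the working, those gains are about 2 and 5 points (4.1% to 5.8% and to 9.2%). No figure stated in the plan is wrong on this account. The change is an optional improvement, worth making because it is cheap and protects the primary decision.

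**What to change.** In REDCap, put the ease-of-use rating and the two video ratings on a page that is saved before any comment field appears. On the next page, show the same short comment prompt for the ease rating whatever the answer. Reasons for 'harder' and 'very hard' are still collected, reasons for the other answers are added, and no endpoint, threshold or sample size changes. Locking the ratings first matters as much as the uniform prompt, because the rating can then no longer be adjusted to avoid a comment.

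The clinician discomfort item may be laid out in the same way for consistency; this has no bearing on the success rule.

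The cost is a revised form and REDCap layout, an IRB submission, and a few extra seconds per form, mostly when the answer is 'same' or better. Keeping the comment to one line limits the added load.
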